2.3 RISK/BENEFIT ASSESSMENT

2.3.1 Known Potential Risks

Niagen has been sold as a dietary supplement in the United States since 2003. Labeling guidelines recommend consumers to limit their intake to 2 capsules/day (250 mg/day). This recommended level is the equivalent of 3.8 mg/kg body weight/day, which is 1000-fold less than the highest dose determined to be safe and well tolerated in rats, and there is no limit on the duration of ingestion.

There is extensive literature on the beneficial effects of NR in animal models,^{12, 13} and multiple lines of non-clinical data suggest that it should be well tolerated in human subjects. In an acute toxicology study, rats that were given a single oral dose (5000 mg/kg) of NR did not show clinical signs of toxicity or mortality (unpublished results). The NR dose proposed for this study is within the doses tested in mice for up to 4 months and is 300-fold below the daily dose that was given in rats in a 14-day dose range finder study. There are also accumulating data on the pharmacokinetics and safety of orally administered NR in humans. Recently, a 2 x 6-week randomized, double-blind, cross-over study was performed to assess the tolerability of chronic NR supplementation and its efficacy for increasing NAD $^{+}$ bioavailability. Here the oral administration of NR 500 mg twice daily (total 1000 mg daily, Niagen, ChromaDex, Inc.) was well tolerated, readily absorbed, and detectable in human plasma, white blood cells, and urine.¹⁴ In a pharmacokinetic study of 8 healthy volunteers at the University of Washington, Seattle, the oral dose of NR dose was escalated from 250 mg daily to 1000 mg twice daily over a 9-day period with a resultant 100% increase in blood NAD $^{+}$ content that highly correlated to NR levels.¹⁵ No adverse events were associated with NR treatment in either of these two published human studies.

Niacin is a form of vitamin B3 and has been used to treat hypercholesterolemia and pellagra for many years. Niacin administration can lead to undesirable effects such as spontaneous flushing, but based on its pharmacology, NR would not be predicted to give this side effect.^{16, 17} Indeed, the incidence of flushing side effect with NR treatment was not different compared with placebo in the double-blind study.¹⁸ Nicotinamide, an expected metabolite of NR, is considered to be of low toxicity in food by several regulatory agencies including the United States Food and Drug Administration (FDA) and the European Food Safety Authority (EFSA). Clinical trials of nicotinamide up to 3000 mg daily and 3 years in patients with or at risk of developing Type 1 diabetes have not reported significant adverse effects.^{19, 20} In addition, doses of 25 and 42 mg/kg body weight per day had no effect on a variety of biochemical parameters including those assessing liver and kidney function.

Abbreviated Title: NR in psoriasis

Version Date: 07/21/2023

In summary, careful analysis of the available information on NR does not reveal any potential serious toxicity that would preclude its use in psoriasis subjects. Given the safety and tolerability of NR in published human studies,^{18, 21} and the favorable experience with NR in our NHLBI DIR protocol (16-H-0129, discussed in Background section), we propose to test the effect of NR in psoriasis patients at a dose 500 mg twice daily, a dose that is less than what is currently approved for use in other active clinical studies of the aforementioned groups.

The only tests and procedures done under this study are skin biopsies (optional), blood draws, and urine collection. The individual study procedure risks are listed below.

Skin biopsy: Two 4mm or smaller biopsies may be collected at visit 1 and visit 2 for a total of four skin biopsies. This procedure will be performed under local anesthesia. The entire procedure takes approximately 20 minutes. Discomfort at the biopsy site is usually mild and transient. This can be treated with minor analgesics. Normally, the risks include a reaction to the local anesthetic and the slight possibilities of local bleeding or infection. Scarring always occurs at the biopsy site.

Phlebotomy: Standard precautions for obtaining human blood samples will be taken. Transient discomfort and minor bruising may occur at the phlebotomy site. Vasovagal symptoms can occur during blood drawing. Blood samples will be obtained by venipuncture. The quantities of blood to be drawn for research purposes will be less than 550ml, which is consistent with the CC policy as provided in Medical Administrative Series (MAS) 95-9 (revised 5/29/12): for adults, no more than 10.5mL/kg or 550ml (whichever is smaller) will be drawn for research purposes over any 8 week period.

Known Potential Benefits

This supplement study has no prospect of direct benefit.

2.3.2 Assessment of Potential Risks and Benefits

The risks of the study supplement and the minor procedures included in this protocol are minimal and justified by the potential benefit of expanding our understanding of how nutrient levels may play a role in the pathophysiology of psoriasis and at the same time employing strategies to mimic caloric restriction/fasting may contribute to disease-amelioration. This supplement has been employed at the same or higher doses in numerous studies without any reported adverse effects.^{14, 18, 21}

3 OBJECTIVES AND ENDPOINTS

OBJECTIVES	ENDPOINTS	JUSTIFICATION FOR ENDPOINTS
Primary		
Evaluate the effect of NR on Th17 biology	The primary outcome will be the change in the T _H 17 cell cytokine IL-17 secretion in response to T-cell differentiation comparing the baseline to NR response.	NR blunts Th1 and Th17 activation in naïve and differentiated T cells and psoriatic subjects exhibit elevated IL-17 responsiveness, which is a consistent signature of this

Abbreviated Title: NR in psoriasis

Version Date: 07/21/2023

OBJECTIVES	ENDPOINTS	JUSTIFICATION FOR ENDPOINTS
Exploratory Explore whether other inflammatory components linked to psoriasis are affected by NR.	Evaluate the effect of NR on the T cell transcriptome Explore the effect of NR on neutrophils, specifically low-density granulocytes	The primary driver of psoriasis does appear to be disease. Th17, however, other immune signals and cell types are linked to psoriasis including, neutrophil activation, skin keratinocyte activation and the accumulation of HDL in monocytes/macrophages is proposed to trigger inflammatory pathways. We will explore the effect of NR on modulating these cell types and pathways as exploratory end points

4 STUDY DESIGN

4.1 OVERALL DESIGN

This study is a pilot, prospective, two-arm double-blind, placebo-controlled study where subjects immunological profile will be studied at baseline and following 4 weeks of supplementation with NR or placebo. The allocation of NR: placebo will be 2:1. All enrolled subjects will receive NR or placebo and following 4 weeks of supplement or placebo intake, research parameters will be compared to baseline to determine the effects of this intervention.

SCIENTIFIC RATIONALE FOR STUDY DESIGN

This is a pilot study and the number of subjects were chosen to allow us to have sufficient samples to use RNAseq analysis to explore the effects of NR on T cell biology if the primary outcome of the study is confirmed.

4.2 JUSTIFICATION FOR DOSE

Recently, a 2 x 6-week randomized, double-blind, cross-over study was performed to assess the tolerability of chronic NR supplementation and its efficacy for increasing NAD⁺ bioavailability by investigators at the University of Colorado, Boulder.¹⁴ They demonstrated that the oral administration of NR 500 mg twice daily (total 1000 mg daily, Niagen, ChromaDex, Inc.) was well tolerated, readily absorbed, and detectable in human plasma, white blood cells, and urine.

Abbreviated Title: NR in psoriasis

Version Date: 07/21/2023

5. STUDY POPULATION

ELIGIBILITY ASSESSMENT AND ENROLLMENT

All protocol eligibility criteria will be met before dispensing study medication to participants or conducting the biopsy for the baseline visit. Patients will sign the consent prior to any screening tests/procedures done as part of this protocol.

5.1 INCLUSION CRITERIA

Individuals must meet all inclusion criteria listed below in order to be eligible to participate in the study.

- Males and females between the ages of 18 and 80 with mild to moderate active psoriasis.
- Female subjects of child-bearing ability willing to commit to reliable contraception while participating in the study.
- Ability to provide informed consent
- Willingness and ability to participate in required study procedures

5.2 EXCLUSION CRITERIA

- Severe psoriasis by PASI (Psoriasis Area and Severity Index) score > 12
- Currently being treated with biologic immune modifying agents.
- Currently on treatment for allergies or other inflammatory diseases.
- Currently taking a multivitamin, Vitamin B or tryptophan supplementation and unwilling to stop within 2 weeks of baseline visit..
- Unwillingness/inability to provide informed consent
- ALT > x3 upper limit of normal, hepatic insufficiency or active liver disease
- Recent history of acute gout
- Chronic renal insufficiency with creatinine > 2.5mg/dl
- Pregnant (or attempting to become pregnant) women
- Current participation in another drug study
- History of intolerance to NR precursor compounds, including niacin or nicotinamide
- Study adherence concerns
- Individuals with diabetes type 1 and 2 who use insulin
- Women of child-bearing potential unwilling to use contraception or unwilling to practice abstinence
- Breastfeeding women unwilling to stop breastfeeding
- Immunization administered within 30 days of participation and no plans for immunization while participating in the study

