7.2 PARTICIPANT DISCONTINUATION/WITHDRAWAL FROM THE STUDY

Participants are free to withdraw from participation in the study at any time upon request. An investigator may discontinue or withdraw a participant from the study for the following reasons:

- 1) Subject taking less than 75% of their capsules
- 2) Subject found to be pregnant or wishes to breastfeed during the study will automatically be withdrawn
- 3) If subject no longer wish to participate
- 4) Subject's non-compliance or per PI discretion for development of a condition that may independently affects immune activity.

Prior to removal from study, any subject who has started the study intervention should complete a safety visit. For subjects who complete the study, this would be included in Visit 2. If a subject requests withdrawal early for any reason, we will make every effort to have them complete an

Abbreviated Title: NR in psoriasis

Version Date: 07/21/2023

unscheduled safety visit..

The reason for participant discontinuation or withdrawal from the study will be recorded in the source document. Subjects who sign the informed consent form and are randomized but do not receive the study intervention may be replaced. Subjects who sign the informed consent form, and are randomized and receive the study intervention, and subsequently withdraw, or are withdrawn or discontinued from the study, will be replaced until the recruitment goals of 18 NR and 9 placebo subjects have completed the protocol. Participants who are withdrawn for reasons that are temporary, such as an infectious disease or administration of an immunization, may be re-screened and if they meet eligibility then re-enrolled with a new study id.

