9.4 STATISTICAL ANALYSES

9.4.1 General Approach

9.4.2 Analysis of the Primary Endpoints

The primary outcome will be the change in the T_H17 cell cytokine IL-17 secretion in response to T-cell differentiation comparing baseline levels versus their respective response to NR or placebo. The comparisons will be performed using paired two-tailed Student t-tests or if the data is not normally distributed, by the Wilcoxon test. Significance will be tested at the 0.05 alpha level in this pilot study.

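### Section 7.2 treats infection and immunization alike as temporary reasons for withdrawal, but 5.2 has a baseline criterion only for immunization, so a baseline IL-17 sample taken during an acute infection can enter the primary endpoint

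*Combined protocol and SAP*

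**What the plan says.** Section 5.2 touches immune state at entry in several places. It excludes current biologic treatment, and its general inflammation item is "Currently on treatment for allergies or other inflammatory diseases". It also lists "Immunization administered within 30 days of participation", "Recent history of acute gout" and "hepatic insufficiency or active liver disease". No item names a current or recent infection.

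Section 7.2 opens with "An investigator may discontinue or withdraw a participant from the study for the following reasons". One of those reasons is "per PI discretion for development of a condition that may independently affects immune activity". It then adds: "Participants who are withdrawn for reasons that are temporary, such as an infectious disease or administration of an immunization, may be re-screened", with re-enrolment under a new study ID if eligibility is met. Participants who have received study product and leave are replaced until 18 NR and 9 placebo participants have completed.

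Section 8.1 lets the screening visit be combined with Visit 1. The schedule in 1.3 allows up to 120 days for screening. It places hs-CRP and a CBC with differential at both baseline and Day 28, but no eligibility or analysis rule uses either to judge infection.

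The primary outcome is the change in IL-17 secretion on T-cell differentiation. Section 9.4.2 tests it against each arm's own baseline: "The comparisons will be performed using paired two-tailed Student t-tests", or a Wilcoxon test if the data are not normal. Section 9.2 computes power for a two-sample t-test of the changes between arms.

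**The concern.** Section 7.2 names infection and immunization together as temporary reasons to take someone out. Section 5.2 matches only one of them at entry. An acute infection present at the baseline draw passes every listed criterion, whereas one that develops later can lead to withdrawal and replacement. Re-screening has the same gap: re-enrolment depends on the 5.2 criteria, and none of them asks whether the infection that caused the withdrawal has resolved.

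The endpoint is a change from baseline, so disturbance at one end of the interval matters. If infection raises stimulated IL-17 output, some baselines are too high and the Day-28 values, after removals, less so. Both arms then show a fall without any NR effect, and a paired test within the NR arm can read that fall as a response. If infection lowers the output, the drift runs the other way and can hide an effect. In an NR-versus-placebo comparison the drift cancels on average, but the extra spread remains.

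**Working it through.** **Inputs from the documents (9.2).** SD of change 185.74 pg/ml; 18 NR and 9 placebo; two-sided alpha 0.05; differences of 329 and 229 pg/ml.

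**Assumed, not in the documents.** A share p of participants has a transient baseline rise of d pg/ml that is gone by Day 28.

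**Step 1: reproduce the plan's power.** For the two-sample t-test the noncentrality is difference / [SD × √(1/n₁ + 1/n₂)].
- 18 + 9: standard error 185.74 × √(1/18 + 1/9) = 75.8. Then 329/75.8 = 4.34 gives 98.6%, and 229/75.8 = 3.02 gives 82.7%.
- 16 + 8: 97.4% and 77.7%.
- Stated: 98%, 82%, 97% and 77%. All four agree, so the planning test is the between-arm t-test.

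**Step 2: effect of a disturbed baseline.** With no NR effect and every affected Day-28 participant removed:
- mean drift = −p × d
- SD of change = √(185.74² + d² × p × (1 − p))

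With d = 300:
- p = 5%: drift −15, SD √(34,499 + 4,275) = 196.9
- p = 10%: drift −30, SD √(34,499 + 8,100) = 206.4
- p = 15%: drift −45, SD √(34,499 + 11,475) = 214.4

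**Step 3: rejection rates by simulation** (100,000 trials per setting; repeat runs differ by a few tenths of a point). In the half-removal column the same share p is affected at Day 28 and half of those are removed. The power columns assume full removal.

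| p (d = 300) | NR-arm paired false positives, all removed | same, half removed | Between-arm power, 229 pg/ml | Between-arm power, 329 pg/ml |
|---|---|---|---|---|
| 0 | 5.0% | 5.0% | 82.7% | 98.6% |
| 5% | 5.7% | 5.3% | 78% | 97% |
| 10% | 8.3% | 5.8% | 74.5% | 96% |
| 15% | 12.5% | 6.6% | 71% | 95% |

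The between-arm false-positive rate stays at about 5% throughout. With d = 150 and full removal, paired false positives are 5.3% to about 7.5%, and power for 229 pg/ml is about 81% to 80%.

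**Step 4: why a common drift does not look common under 9.4.2.** The mean change needed for significance is t × SD/√n. In the NR arm this is 2.110 × 185.74/√18 = 92 pg/ml. In the placebo arm it is 2.306 × 185.74/√9 = 143 pg/ml. The same drift is therefore more likely to be called significant on NR than on placebo.

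**The case against.** The strongest reply is that the bias belongs to the analysis and not to eligibility. The trial is blinded and placebo-controlled with the same rules in both arms, so any drift is shared. It biases the result only because 9.4.2 tests within arm while 9.2 plans a between-arm test. This stands: a between-arm test removes the bias with no change to 5.2. What it does not remove is the added variance.

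Four stronger readings are tempting, and the documents do not support them.

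- **That a drift is built in.** Withdrawal in 7.2 is permitted and discretionary; only replacement is firm. With half the affected Day-28 participants removed, most of the inflation disappears. Nothing in the documents shows that infection moves IL-17 secretion by differentiated T cells, or in which direction. The illustrative 300 pg/ml is half the 600 pg/ml starting mean in 9.2 and close to the whole 329 pg/ml effect.
- **That the rule reverses at baseline.** Section 7.2 is not confined to the time after baseline. A subject counts as enrolled once consent is complete (10.1.3), and 7.2 covers people randomised but not yet treated. A condition arising between consent and the baseline draw can already be handled there. The gap is a condition already present at consent or re-screening.
- **That 5.2 screens immune disturbance only through treatment and immunization.** Recent acute gout and active liver disease are excluded whether treated or not.
- **That untreated chronic inflammation causes the drift.** Such a condition is present at both visits and largely cancels in a paired change. The mechanism needs a transient condition.

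**Conclusion.** The mismatch between 5.2 and 7.2 on acute infection is real and should be reconciled. Its consequence is a possible drift, not a demonstrated one.

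The size depends on the assumed rise, the assumed share affected, and how often the investigator uses the withdrawal option. Over the range examined it runs from negligible (150 pg/ml, few affected) to a paired false-positive rate of about 12.5% in the NR arm (300 pg/ml, 15% affected, every affected Day-28 participant removed). Between-arm power for 229 pg/ml falls by about 5 to 12 points at 300 pg/ml. For the planned 329 pg/ml it stays at about 95% or more.

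A reader might infer that the NR-versus-placebo result would itself be biased. Under rules common to both arms it would not be; it would only be less precise. The within-arm analysis in 9.4.2 is the larger problem, and this gap adds to it.

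**What to change.** 1. **Section 5.2.** Add one item: the baseline research draw and randomisation are deferred while a temporary condition that 7.2 treats as affecting immune activity, such as an infection, is present. Say that it also applies at re-screening. The visit moves within the existing 120-day screening window, and the sponsor sets the interval.
2. **Analysis.** Add a sensitivity analysis of the primary endpoint that omits participants affected at either visit, with the hs-CRP and CBC with differential already drawn at both visits as documentation.
3. **Section 9.4.2.** Make the primary test a between-arm comparison of the changes, consistent with 9.2. This is the main protection against any drift shared by the arms.
4. **Visit 2.** The 7.2 withdrawal wording needs to be reconciled with the visit window (±7 days, 1.3), the dosing allowance (±5 days, 6.1.6) and the collection window (±48 hours, 8.2.2). This review does not say which should govern.

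Cost: one eligibility line, one sensitivity analysis, a corrected sentence in 9.4.2 and the reconciliation of the Visit 2 passages. Some baseline visits will be postponed. No extra participants or procedures are needed.

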5.3 INCLUSION OF VULNERABLE PARTICIPANTS

Rationale for the Exclusion of Children

Subjects under 18 years of age will not be considered for inclusion in this protocol because there is no direct benefit from participating in this study and the volumes of blood levels drawn exceed

Abbreviated Title: NR in psoriasis

Version Date: 07/21/2023

minimal risk for children

Rationale for the exclusion of pregnant women

The subject must not be pregnant or actively seeking pregnancy in order to participate in this study. NR has not been determined to be safe in pregnancy or breastfeeding women. A recognized form of contraception must be used by subjects while enrolled. Contraception use will be determined during telephone screening and confirmed at the screening visit.

Rationale for the exclusion of cognitively impaired subjects

Subjects with cognitive impairment will not be considered for inclusion because there is no direct benefit from participating in this study.

5.4 LIFESTYLE CONSIDERATIONS

During this study, participants are asked to:

- Refrain from making major changes in dietary intake or physical activity during the 6 weeks of active study participation.

5.5 SCREEN FAILURES

Screen failures are defined as participants who consent to participate in the clinical trial but are not subsequently assigned to the study intervention. These subjects will sign consent and will receive a study id.

Individuals who do not meet the criteria for participation in this trial (screen failure) may be rescreened at a later date at PI discretion. Individuals who do not meet criteria for participation based on an abnormal laboratory test result may be rescreened after one month.

Rescreened participants will be assigned a new participant id number from the initial screening.

5.6 STRATEGIES FOR RECRUITMENT AND RETENTION

Subjects with mild to moderate psoriasis will be recruited from [name] psoriasis clinic. We will also recruit subjects through NIH using traditional recruitment methods such as referrals from other protocols, outside physician referral and self-referral.

With IRB approval the study may opt to use the following strategies for recruitment of patients:

- ClinicalTrials.gov
- Clinical Center Research Studies website
- National Heart, Lung and Blood Institute (NHLBI) patient recruitment website
- Twitter messages and chats with study investigators
- Social Media posts
- Use of CC Office of Patient Recruitment services including creation and distribution of study flyers and information through pre-existing recruitment avenues such as the NIH recruitment listserv.

Abbreviated Title: NR in psoriasis

Version Date: 07/21/2023

We expect to screen up to 40 subjects with a goal of 27 subjects (18 NR + 9 placebo) completing the study.

5.6.1 Costs

There will be no anticipated costs that the subject will be responsible for.

5.6.2 Compensation

Subjects will be compensated for some of the procedures that are performed since they may not provide direct benefit to the subject. They will be compensated by check or direct deposit at the end of the study or at the time of study withdrawal for the procedures completed. Payment will typically be received within 2 months of the last study visit.

Procedures	Convenience Units	Compensation per procedure	Frequency	Total Compensation
Medical History	2.5	\$25.00	1	\$25.00
Screening Blood Draw (if needed)	1	\$10	1	\$10
Research Blood Draw	5	\$50.00	2	100.00
Research skin biopsy	5	\$50.00	4	\$200.00
Drug administration, General	2	\$20.00	28	\$560.00
Maximum Compensation:				\$895.00

Reimbursement for travel, food, and lodging will not be provided.

